3.3.2 Exclusion Criteria (any of the following factors will result in ineligibility)

- 1) Patients who have unstable or recent unstable cardiac syndrome as defined by:
 - a. Severe heart failure (*NYHA IV*) or angina (*CCS class IV*) symptoms.
 - b. Critical left main (*LM*) coronary disease.
 - c. Hospitalization for arrhythmias, *CHF* or acute coronary syndrome prior to randomization.
- 2) Patients who have severe left ventricular obstructive disease as defined by:
 - a. Severe aortic or mitral stenosis (aortic or mitral valve area $<1.0\text{cm}^2$ or mean gradient $> 40\text{ mmHg}$ or $> 10\text{mmHg}$ respectively)
 - b. Dynamic left ventricular (*LV*) outflow obstruction.
- 3) Patients who have demonstrated exercise induced ventricular arrhythmias or have experienced a recent hospitalization for arrhythmias.
- 4) Patients who have cognitive deficits that would preclude rehabilitation.
- 5) Patients who have physical limitations that would preclude rehabilitation. (Unless they have agreed to participate in the follow-up registry)
- 6) Patients who are unable to attend the *Prehab* program. (Unless they have agreed to participate in the follow-up)

3.4 Operational Definitions

3.4.1 Baseline Clinical Characteristics

Preoperative patient demographics, cardiac risk profile, procedure data, surgical risk scores (*EuroSCORE II* and *STS-PROMM*(50)(51)(52)), medical history and medication profile, cardiac risk factors

“The PREHAB Study” (Pre-operative Rehabilitation for reduction of Hospitalization After coronary Bypass and valvular surgery.)

and cardiac illness severity are routinely collected for all patients in the pre-existing site surgical databases which will be utilized for this study. Each site will also collect co-variates of co-morbidities (*Charlson Co-morbidity Index*, *Functional Co-morbidity Index* (53), *OARS scale* for activities of daily living (*ADL*) and instrumented activities of daily living (*IADL*)(54) as well as postoperative complications and postoperative hospital *LOS*. In order to avoid issues caused by delayed hospital discharge due to non-medical reasons, patients will be evaluated daily for “readiness for discharge” using a standardized set of criteria. Cognitive function will be measured using the Montreal Cognitive Assessment (*MoCA*) (43)(44)(45).

3.4.2 Frailty Assessments

Our strategy for rapid screening of frailty in a large volume of clinic patients will be to use the 9-point Clinical Frailty Scale (*CFS*) (56)(See *Figure 4* and appendix). The *CFS* is the simplest tool to implement at multiple centres, has a high inter-observer reliability and shows good performance (by *ROC analysis*) for risk of death or institutionalization. Due to the need to screen a large number of individuals (785 patients; *Figure 5*) the use of the *Modified* and *SPPB* are less practical to implement as routine practice in the outpatient clinic sites. Therefore our approach is to use a *CFS* score of ≥ 3 as the initial indication of frailty (57) . This approach will allow us to estimate degrees of frailty in a large volume of patients in a rapid, cost-effective and highly feasible manner. All enrolled patients will be further assessed using the modified Fried criteria(33)(32)(34), and a reduction of frailty will be defined as a binary value (i.e. frail/non-frail) using these criteria(33)(32)(34).

The *SPPB* criteria will be used as a third measure.(46) As a fourth measure, our data collection protocol will also enable a Frailty Index (*FI*) calculation.(29)(56)(58)(30) The inclusion of the more definitive frailty evaluations are intended to gain more information about the different domains of frailty in the elderly to further improve the clinical frailty assessments that will be used in the future. To ensure reliability of this approach, we have compared the three measures of frailty (*CFS*, *Modified* and *SPPB*) on 169 elective cardiac surgery patients at the St. Boniface Hospital. The spearman correlation was ~ 0.65 for all three comparisons and the Cohen’s Kappa, which is a concordance measure between the different frailty definitions is ~ 0.50 . These values indicate a moderately strong link between all three measures; however it is possible that they capture somewhat different domains of frailty.

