3.1.1.1 Frailty in the Cardiac Surgery Population at St. Boniface Hospital

We undertook a systematic review of frailty in the elderly undergoing cardiac surgery (see *Table 2 & Table 3*).(23)(24)(25)(26)(27)(28)(29)(30)(31) This review demonstrated an association with increased frailty and a major negative outcomes ranging from increased institutional care to major adverse cardiac and cerebral event (*MACCE*) and increased in-hospital and long-term mortality after cardiac surgery. However, the lack of a standardized and comprehensive definition of frailty in these studies prevents clarity in understanding the interaction of frailty in the elderly and cardiac surgery. We subsequently completed a prospective examination of frailty in 133 consecutively consenting elderly cardiac surgery patients with high-levels of co-morbid disease (See *Table 4*, *Table 5*, *Table 6* and *Figure 2*). Two definitions of frailty were used (see *Appendix I*): (1) *Modified Fried criteria*: (32)(33)(34) a patient was deemed “frail” if they met ≥ 3 of the following 7 criteria: slowness (5m gait speed)(35), weakness (handgrip strength measurement)(36) and questionnaires assessing self-reported weight loss, exhaustion (the two-item Center for Epidemiologic Studies Depression (*CES-D Scale*), depression (the 5-point geriatric depression scale (*5-GDS*))(37)(38)), low physical activity (the Paffenbarger Physical Activity Index(39)(40)(41)(42)), and cognitive impairment (the Montreal Cognitive Assessment (*MoCA*))(43)(44)(45)). (2) *Short Physical Performance Battery (SPPB)*: a patient was deemed “frail” if his/her composite score was ≤ 9 based on 5m gait speed, balance tests, and the repeated chair stand test (each scored from 0 to 4)(46). Using the modified Fried or the SPPB criteria, 72 (54.1%) or 69 (51.9%) (respectively), patients studied were deemed frail (See *Table 3*). Frail patients were older, more commonly female, had higher *EuroSCORE II* values (a cardiac surgery specific mortality risk prediction score) and lower self-health ratings. Diabetes, cerebrovascular disease (*CVD*), chronic obstructive pulmonary disease (*COPD*), arthritis, anemia, peripheral vascular disease (*PVD*), and lower serum albumin were also significantly associated with being frail. Notably, frailty correlated with clinically important measures of increased hospital *LOS*: total adjusted hospital *LOS* (median 6 days (IQR: 5 – 9) in non-frail vs. 8 days (IQR 6 – 12) in “frail” patients, $p < 0.001$) and a greater proportion of patients in hospital > 7 days (37.7% in non-frail vs. 58.3% in frail patients, $p < 0.02$; See *Table 4 & Table 5*). This longer hospital stay amongst frail patients has implications for increased healthcare costs and we have observed an association between new and persistent mood disorders and reduced engagement in postoperative physical activity with a hospital *LOS* > 7 days after cardiac surgery.

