3.3 Eligibility Criteria

3.3.1 Inclusion Criteria (all need to be fulfilled for eligibility)

- 1) Patients, aged 60 years or older, undergoing elective isolated coronary artery bypass grafting (*CABG*), aortic valve repair/replacement for moderate aortic stenosis or severe regurgitation, mitral valve repair/replacement for moderate stenosis or severe regurgitation or combined *CABG*/valve procedures.
- 2) Patients with Clinical Frailty Score (*CFS*) ≥ 3 (managing well) and < 7 (8 = very severely frail, approaching end-of-life or 9 = terminally ill) at time of acceptance for cardiac surgery.
- 3) Patients with an estimated ≥ 4 week wait time.

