5.1.2 Secondary Outcomes

(1) pre-operative frailty, (2) exercise capacity, (3) physical activity behavior, (4) in-hospital outcomes, (5) 1-year clinical outcomes, (6) 1-year health-related quality of life, (7) cost-analysis.

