5.2 Statistical/Analytical Plan

Objective 1: To determine if *Prehab* reduces the proportion of frail elderly patients requiring a prolonged hospital length of stay of >7 days. A univariable analysis will be undertaken to determine if hospital *LOS* > 7 days is associated with frailty and other patient-level factors. A stepwise multivariable logistic regression model will then be developed to determine if *Prehab* attendance is independently associated with a decreased risk of prolonged hospital length of stay > 7 days. As a secondary analysis, hospital *LOS* will also be compared as a continuous variable between the *Prehab* and standard care groups using a Mann-Whitney test.

“The PREHAB Study” (Pre-operative Rehabilitation for reduction of Hospitalization After coronary Bypass and valvular surgery.)

Objective 2: Does attending *Prehab* influence frailty, exercise capacity, physical activity behavior, in-hospital complications, and *HRQoL*? Although we will employ four different measures of frailty, based on our preliminary data and based on a Task Force’s position statement(90), the Modified Fried Criteria will be the primary frailty outcome over time from baseline to the end of *Prehab* program (pre-operatively), or from baseline to the 3-month post-operative follow-up. The primary measure of exercise capacity will be the *6MWT* and will be analysed with univariable linear regression models to evaluate the association between the *6MWT* and *Prehab* attendance. Accelerometers will be used to objectively measure the number of minutes spent performing moderate to vigorous physical activity (*MVPA*) and total physical activity (*TPA*) per day for a period of 7 days and compared between groups. A composite outcome for a major adverse cardiac event (i.e. *MACCE* = in-hospital stroke, myocardial infarction, renal failure requiring dialysis and death) and delirium will be compared between groups using a Chi-Square or Fisher’s Exact test. A multivariable logistic regression will be used to identify if *Prehab* is independently associated with in-hospital delirium. The *SF-12v2* and *EQ-5D* scores, after normative standardization, will be analyzed through use of a repeated *ANOVA* to allow for a standardized group and group/time interaction effect estimation.

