Appendix I - Modified Fried Criteria (1-7)

Frailty Domain	Method of Measurement	Cutoffs for Measurement
1 Slowness	4-meter gait speed Measures the time required to walk 4 meters at a normal pace (use the best of two times)	<4.82 sec: 4 pt 4.82-6.20 sec: 3 pt 6.21-8.70 sec: 2 pt >8.7 sec: 1 pt Unable: 0 pt
2 Weakness	Handgrip strength The patient is asked to squeeze the handgrip dynamometer as hard as possible, this is repeated 3 times (with each hand and then with the strongest hand) and the maximum value is recorded	Sex- and BSA-based cutoff ♂: ≤24 kg/m ² : ≤29 kg 24.1-28 kg/m ² : ≤30 kg ♂: >28 kg/m ² : ≤32 kg ♀: ≤26 kg/m ² : ≤17 kg 26.1-29 kg/m ² : ≤18 kg ♀: >29 kg/m ² : ≤21 kg Simplified cutoff ♂: ≤30 kg ♀: ≤20 kg
3 Low physical activity	PASE & Paffenbarger Physical Activity Questionnaire	♂: <383 kcal/week ♀: <270 kcal/week
4 Weight loss	Self-reported	>10 pounds or >5% in past year
5 Exhaustion	a) 2 questions from CES-D: How often in the last week did you feel this way: i. I felt that everything was an effort ii. I could not get going	Positive if answered either question Most of the time or Moderate amount of the time
6 Cognitive impairment	Montreal Cognitive Assessment (MoCA) Trails A and B	Score <26/30
7 Depressed mood	Geriatric depression scale (5-item)	Score ≥2/5
≥3 Criteria Required for Diagnosis of Frailty		

“The PREHAB Study” (Pre-operative Rehabilitation for reduction of Hospitalization After coronary Bypass and valvular surgery.)

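### The main frailty outcome is reduced to frail/non-frail and given two alternative time points; the pre-operative count of Modified Fried criteria, adjusted for baseline, would use the same data better

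*Combined protocol and SAP*

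**What the plan says.** **Definition.** Section 3.4.2 states that "a reduction of frailty will be defined as a binary value (i.e. frail/non-frail) using these criteria". Appendix I sets the cut: "≥3 Criteria Required for Diagnosis of Frailty", out of seven.

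**Time point and analysis.** Section 5.2 (Objective 2) says that "the Modified Fried Criteria will be the primary frailty outcome over time from baseline to the end of" the programme, and then offers an alternative: "pre-operatively), or from baseline to the 3-month post-operative follow-up". It does not choose between the two windows. It names a method for length of stay, the 6-minute walk, major adverse events, delirium and quality of life, but none for frailty. Section 5.1.2 puts "1) pre-operative frailty" first among the secondary outcomes, and the Study Synopsis and section 2.4 list the same item.

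**Entry.** Section 3.3.1 requires a CFS of "≥ 3 (managing well") and below 7. No criterion requires Fried frailty; section 3.4.2 has the Fried assessment done in patients already enrolled. It reports a kappa of about 0.50 between the frailty definitions.

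**Preliminary data.** In the 133-patient cohort of section 3.1.1.1, by the Modified Fried and SPPB criteria in turn, "72 (54.1%) or 69 (51.9%) (respectively), patients studied were deemed frail".

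**The concern.** Making patients less frail before surgery is the trial's stated mechanism. If length of stay turns out neutral, this outcome should tell readers whether the programme failed to change frailty, or changed it without shortening the stay. A coarse, loosely specified outcome does that poorly, for three reasons.

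- Crossing one threshold is a crude measure of change. A fall from 6 criteria to 3 counts as nothing, while a fall from 3 to 2 counts as success.
- Patients are selected on one scale and judged on another, so some may start on the non-frail side of the outcome's threshold.
- Two windows and no named test leave the choice open until the data are seen. The windows also ask different questions. The pre-operative one isolates the programme. The 3-month one mixes in surgery and post-operative rehabilitation, to which both arms are referred (section 3.5.2).

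**Working it through.** **1. The plan's own figures.** The preliminary Fried share reproduces: 72/133 = 54.1%, leaving 61/133 = 45.9% not frail. The sample size in section 5.3 also reproduces, for length of stay only. With 58.3% against 38.3%, two-sided 5% and 80% power:

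n = [1.96·√(2 × 0.483 × 0.517) + 0.8416·√(0.583 × 0.417 + 0.383 × 0.617)]² / 0.20² = (1.385 + 0.583)² / 0.04 ≈ 96.8, so 97 per arm.

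With 20% dropout, 97/0.8 = 121.25, so 122 per arm and 244 in all. The documents give no effect size or power for frailty.

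**2. How many patients might not be Fried-frail at entry.** No share is stated for CFS-selected patients. It can be bracketed from kappa = 0.50 and Fried prevalence f = 0.541, for an assumed CFS-positive prevalence c:

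- chance agreement pe = fc + (1 − f)(1 − c)
- observed agreement po = 0.5 + 0.5·pe
- positive on both, a = (po − 1 + f + c)/2
- non-frail share among CFS-positives = 1 − a/c

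| c (assumed) | pe | po | a | Not Fried-frail | Of 244 |
|---|---|---|---|---|---|
| 0.45 | 0.496 | 0.748 | 0.370 | 18% | 44 |
| 0.541 | 0.503 | 0.752 | 0.417 | 23% | 56 |
| 0.75 | 0.521 | 0.760 | 0.526 | 30% | 73 |

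The 45.9% in the preliminary cohort, which is not described as CFS-selected, is a rough upper bound (0.459 × 244 = 112).

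**3. Cost of the threshold in general.** For a normal variable split at proportion q, the binary version keeps φ(z)²/[q(1 − q)] of the information. This is 63% at 54/46 and 52% at 77/23.

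**4. Power for each analysis.** Assumptions, none from the documents: 97 per arm, correlated normal scores rounded to 0–7, SD 1.6, correlation 0.6 between visits, 55% to about 75% Fried-frail at baseline, two-sided 5%.

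| Analysis | Benefit 0.5 criterion | Benefit 0.75 criterion |
|---|---|---|
| Frail-to-non-frail reversion | 25–30% | 48–58% |
| Frail status at follow-up, unadjusted | 38–41% | 71–75% |
| Frail status, adjusted for baseline count | 44–50% | 80–84% |
| Count, unadjusted | 55–58% | 89–91% |
| Count, adjusted for baseline count | 73–74% | 97–98% |

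These are simulation results, good to a few points. Like for like at a benefit of 0.5, dichotomising costs about 14–20 points without adjustment (55 − 41 to 58 − 38) and about 23–29 points with it. At 0.75 the costs are 14–20 (89 − 75 to 91 − 71) and 13–18 (97 − 84 to 98 − 80).

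**5. Two windows.** If both are tested at 5%, the chance of at least one false positive is 1 − 0.95² = 9.75% if independent, and 9.5% to 7.0% for correlations of 0.3 to 0.9.

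**The case against.** A reader might infer three stronger things, and the documents support none of them.

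- *Patients who enter non-frail cannot have the outcome.* Section 3.4.2 speaks of a binary frail/non-frail value and section 5.2 of an outcome over time. Both fit a comparison of frail status at follow-up. Patients who enter non-frail then contribute, since they may become frail while waiting, and the Executive Summary expects waiting patients to weaken.
- *Nearly half of the trial's patients are affected.* The 46% comes from a cohort not described as CFS-selected. The CFS cut-off behind the kappa is not given, and that kappa comes from a different set of 169 patients, so even the 18–30% is an inference.
- *Dichotomising costs the whole gap between 25–30% and 73–74%.* That contrast sets an unadjusted binary test against a baseline-adjusted count. Part of the gap is covariate adjustment, which a binary outcome can also use.

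Other points for the plan are fair. The cut at 3 is the one its own data link to the primary outcome (stay over 7 days in 58.3% of frail and 37.7% of non-frail patients, Table 6). Graded measures are collected as well: SPPB, a Frailty Index and the 6-minute walk. A count weights seven unlike items equally, and weight loss over the past year may hardly move in 4–8 weeks. The Synopsis and sections 2.4 and 5.1.2 already point to the pre-operative assessment, so the 'or' may be loose wording.

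These points limit the concern without removing it. Section 5.2 still makes the Modified Fried criteria the main frailty measure, with two windows and no test, and the count had more power than either binary form in every setting examined.

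**Conclusion.** The point holds as a cheap improvement to a secondary outcome. The binary definition, the absence of a Fried entry criterion, the two windows and the missing test are all in the text. Whether patients who are non-frail at entry can have the outcome depends on a reading that the plan leaves open, and their share is not stated. On either reading graded change is discarded: like for like, about 14–29 points of power at a benefit of 0.5 criterion and 13–20 points at 0.75. These sizes rest on an assumed SD, correlation and uniform benefit. The ordering of the analyses is firmer than the percentages. The primary outcome and the 97 per arm are not affected.

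**What to change.** In sections 3.4.2 and 5.2:

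- Name the pre-operative assessment as the single time point for the main frailty outcome, in line with section 5.1.2.
- Define that outcome as the number of Modified Fried criteria met (0–7). Compare it between randomised arms by linear or ordinal regression adjusted for baseline count and site, in all randomised patients.
- Report pre-operative frail/non-frail status, adjusted for baseline, and the 3-month count as supportive.

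Any count or cut needs a yes/no rule for each item. Appendix I scores slowness 0–4 points on a 4-metre walk without marking which scores count as positive, while section 3.1.1.1 describes a 5-metre gait speed, so that item should be settled in the same edit.

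The cost is wording. Section 3.5.2 already has frailty scores collected at baseline, before surgery and at three months. The downside is that a difference in number of criteria is less intuitive than a proportion and weights the seven items equally, which is why the binary result stays as supportive.

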3.4.3 In-Hospital Outcomes

Postoperative *ICU* and hospital *LOS*, 30-day mortality, major adverse events (death, *MI*, stroke or renal failure requiring dialysis) will be collected using existing site surgical databases. Post-operative *CR* enrollment will be assessed using administrative data from the participating *CR* centers.

In our preliminary analysis, we have identified a strong association between frailty and the occurrence of delirium (Table 5). The participating Cardiac *ICUs* currently perform an agitation and delirium assessment once every 8 hours as standard practice. Delirium assessment will be performed in the *ICU* using the Richmond Agitation-Sedation Scale (*RASS*)(59) and the Confusion Assessment Method for the Intensive Care Unit (*CAM-ICU*). (60)(61)(62). As part of standard of care a blood sample will be collected upon placement of the arterial line in the operating room to ascertain the patient’s sodium, potassium, glucose, white blood cell count, hematocrit, creatinine and albumin and this data will also be collected.(49)(65)

3.4.5 Three-Month Clinical Outcomes and Health-Related Quality of Life (HRQoL)

The EuroQual-5D (*EQ-5D*)(66) will be administered preoperatively and at 12 weeks (time of routine surgical follow-up). The *EQ-5D* is a validated measures of *HRQoL* and was selected due to its simplicity and proven clinical relevance. (67)(68)(69)

“The PREHAB Study” (Pre-operative Rehabilitation for reduction of Hospitalization After coronary Bypass and valvular surgery.)

3.4.6 One-Year Clinical Outcomes and Health-Related Quality of Life (HRQoL)

The EuroQual-5D (*EQ-5D*) will be administered preoperatively and at 1 year following surgery. The *EQ-5D* is a validated measures of *HRQoL* and was selected due to its simplicity and proven clinical relevance.

3.4.7 Physical Activity

We will assess exercise capacity using a 6-minute walking test (*6MWT*). The *6MWT* is a practical and simple test that has a negative correlation between total distance walked and length of hospital stay ($r = -0.62$) (70) and is suitable for use amongst patients with moderate-severe heart and lung disease. (71) Physical activity behavior will be measured using multi-directional accelerometers over a seven-day period, based on the methods described by Colley et al. (72) We have previously used these approaches to assess physical fitness and activity amongst cardiac patients.

3.4.8 Patient Interview Questionnaires/Instruments – The Interview Package

The following questionnaires will be completed at baseline, preoperatively, 3-months following surgery and one year following surgery for both arms of the study. The questionnaires will be administered using the REDCap software with the participant completing the survey on a computer.

1. Seattle Angina Questionnaire (SAQ)
2. Kansas City Cardiomyopathy Questionnaire (KCCQ)
3. Montreal Cognitive Assessment Form (MoCA)
4. 5-Item Geriatric Depression Scale (GDS-5)
5. Generalized Anxiety Disorder 7 Item Scale (GAD-7)
6. OARS Scale for Activities of Daily Living (ADL)/Instrumental Activities of Daily Living (IADL)
7. EuroQol 5-Dimension 5-Level (EQ-5D5L)
8. EuroQol Visual Analog Scale (EQ-VAS)
9. Paffenbarger Physical Activity Scale
10. Nutrition/Exhaustion Questionnaire
11. Self-efficacy for Exercise Questionnaire
12. Baseline Demographics (only done once at baseline)

Patients who prefer to enrol in the registry will not complete any preoperative questionnaires. They will be contacted over the telephone at 3-months and one year following surgery and complete the following questionnaires:

1. Demographic information
2. Generalized Anxiety Disorder 7 Item Scale (GAD-7)
3. Geriatric Depression Scale (GDS)
4. OARS Scale for Activities of Daily Living (ADL)/Instrumental Activities of Daily Living (IADL)

